7.3.2. Bone Biochemical Markers

Baseline, postbaseline, and change from baseline in bone biochemical markers, including urine bicarbonate, urine n-telopeptide, serum c-telopeptides, osteocalcin, bone specific alkaline phosphatase, PTH, vitamin D levels (25-hydroxy) and 1, 25 (dihydroxyvitamin) D levels, fasting serum creatinine and phosphate, spot urine creatinine and phosphate, and renal phosphate threshold (TmP/GFR) will be summarized by treatment group and visit using the Safety Analysis Set. The change from baseline in bone biochemical markers will be compared using the Wilcoxon rank-sum test up to Week 48. Supportive listings for bone biochemical marker measurements will also be provided. For fasting serum and fasting creatinine, only measurements taken when subject was confirmed to be fasting will be reported.

To calculate TmP/GFR, the following formula will be used based on serum creatinine and only for subjects confirmed to be fasting {Barth 2000}:

$$TmP/GFR = TRP \times SPO_4 \quad \text{if } TRP \leq 0.86$$
$$TmP/GFR = 0.3 \times TRP / [1 - (0.8 \times TRP)] \times SPO_4 \quad \text{if } TRP > 0.86$$

where TRP (tubular reabsorption of phosphate) is calculated by:

$$TRP = 1 - \frac{UPO_4}{SPO_4} \times \frac{SCr}{UCr}$$

where SCr is serum creatinine concentration (mg/dL), UPO₄ is urine phosphate concentration (mg/dL), SPO₄ is serum phosphate concentration, and UCr is urine creatinine concentration (mg/dL).

7.4. Renal Safety Analyses

7.4.1. Estimated Glomerular Filtration Rate (eGFR)

Glomerular filtration rate (estimated creatinine clearance) will be calculated using the Schwartz formula for subjects ages 2 to <18 as follows:

$$\text{Schwartz formula (mL/min/1.73 m}^2\text{)} = k \times L/\text{Scr}$$

k is a proportionality constant,

k = 0.55 for pediatric males and females ≥ 2 years to < 12 years;

k = 0.55 for adolescent females ≥ 12-18 years old; and

k = 0.70 for adolescent males ≥ 12-18 years old

L is height in centimeters (cm); and

Scr is serum creatinine (mg/dL).

Summaries of eGFR and change from baseline in eGFR at baseline and at each postbaseline visit will be provided during the double-blind phase. Comparison of change from baseline in eGFR between the 2 treatment groups will be performed using the two-sided Wilcoxon rank-sum test. Median (Q1, Q3) change from baseline in eGFR over time will be plotted.

7.4.2. Confirmed Renal Abnormalities

The following specific renal related laboratory abnormalities will be summarized during the double-blind phase:

- Confirmed (defined as 2 consecutive visits) increase in serum creatinine of ≥ 0.3 mg/dL above baseline
- Confirmed (defined as 2 consecutive visits) increase in serum creatinine of ≥ 0.5 mg/dL above study baseline
- Confirmed (defined as 2 consecutive visits) occurrence of serum phosphorus below 2.0 mg/dL
- Creatinine clearance by Schwartz formula ($CL_{Cr\text{Schwartz}}$) < 50 mL/min
- $CL_{Cr\text{Schwartz}} < 70$ mL/min

If the first of two consecutive results is in the double-blind phase and the second is out of the double-blind phase (ie, in the open-label or TFFU phase), then the result will be considered to be confirmed in the double-blind phase (assuming both values meet the criterion). And if the criterion is met by the last value in the double-blind phase, and no assessments are available after due to the subject exiting the study or data not yet available (eg, due to the data-cut), then the result will also be considered to be confirmed.

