Hyperglycemia, Fasting	110 to 125 mg/dL 6.08 to 6.96 mmol/L	>125 to 250 mg/dL >6.96 to 13.90 mmol/L	>250 to 500 mg/dL >13.90 to 27.79 mmol/L	>500 mg/dL >27.79 mmol/L
Hypocalcemia (corrected for albumin if appropriate*) Adult and Pediatric ≥2 Years	7.8 <LLN mg/dL 1.94 to <LLN mmol/L	7.0 to < 7.8 mg/dL 1.74 to < 1.94 mmol/L	6.1 to < 7.0 mg/dL 1.51 to < 1.74 mmol/L	< 6.1 mg/dL < 1.51 mmol/L
Pediatric ≥7 days -2 Years	7.8 to 8.4 mg/dL 1.94 to 2.10 mmol/L	7.0 to <7.8 mg/dL 1.74 to <1.94 mmol/L	6.1 to <7.0 mg/dL 1.51 to < 1.74 mmol/L	< 6.1 mg/dL < 1.51 mmol/L
Infant, < 7 Days	6.5 to 7.5 mg/dL 1.61 to 1.88 mmol/L	6.0 to < 6.5 mg/dL 1.49 to < 1.61 mmol/L	5.5 to < 6.0 mg/dL 1.36 to < 1.49 mmol/L	< 5.5 mg/dL < 1.36 mmol/L
Hypercalcemia (corrected for albumin if appropriate*) Adult and Pediatric ≥ 7 Days	>ULN to 11.5 mg/dL >ULN to 2.88 mmol/L	> 11.5 to 12.5 mg/dL > 2.88 to 3.13 mmol/L	> 12.5 to 13.5 mg/dL > 3.13 to 3.38 mmol/L	> 13.5 mg/dL > 3.38 mmol/L
Infant, < 7 Days	11.5 to 12.4 mg/dL 2.86 to 3.10 mmol/L	> 12.4 to 12.9 mg/dL > 3.10 to 3.23 mmol/L	> 12.9 to 13.5 mg/dL > 3.23 to 3.38 mmol/L	> 13.5 mg/dL > 3.38 mmol/L
Hypocalcemia (ionized)	3.0 mg/dL to < LLN 0.74 mmol/L to < LLN	2.5 to < 3.0 mg/dL 0.62 to < 0.74 mmol/L	2.0 to < 2.5 mg/dL 0.49 to < 0.62 mmol/L	< 2.0 mg/dL < 0.49 mmol/L
Hypercalcemia (ionized)	> ULN to 6.0 mg/dL > ULN to 1.50 mmol/L	> 6.0 to 6.5 mg/dL > 1.50 to 1.63 mmol/L	> 6.5 to 7.0 mg/dL > 1.63 to 1.75 mmol/L	> 7.0 mg/dL > 1.75 mmol/L
Hypomagnesemia	1.40 to <LLN mg/dL 1.2 to <LLN mEq/L 0.58 to <LLN mmol/L	1.04 to < 1.40 mg/dL 0.9 to < 1.2 mEq/L 0.43 to < 0.58 mmol/L	0.67 to < 1.04 mg/dL 0.6 to < 0.9 mEq/L 0.28 to < 0.43 mmol/L	< 0.67 mg/dL < 0.6 mEq/L < 0.28 mmol/L

CHEMISTRY				
	Grade 1	Grade 2	Grade 3	Grade 4
Hypophosphatemia Adult and Pediatric > 14 Years	2.0 to < LLN mg/dL 0.63 to < LLN mmol/L	1.5 to < 2.0 mg/dL 0.47 to < 0.63 mmol/L	1.0 to < 1.5 mg/dL 0.31 to < 0.47 mmol/L	< 1.0 mg/dL < 0.31 mmol/L
Pediatric 1 Year–14 Years	3.0 to < LLN mg/dL 0.96 to < LLN mmol/L	2.5 to < 3.0 mg/dL 0.80 to < 0.96 mmol/L	1.5 to < 2.5 mg/dL 0.47 to < 0.80 mmol/L	< 1.5 mg/dL < 0.47 mmol/L
Pediatric < 1 Year	3.5 to < LLN mg/dL 1.12 to < LLN mmol/L	2.5 to < 3.5 mg/dL 0.80 to < 1.12 mmol/L	1.5 to < 2.5 mg/dL 0.47 to < 0.80 mmol/L	< 1.5 mg/dL < 0.47 mmol/L
Hyperbilirubinemia Adult and Pediatric > 14 Days	> 1.0 to 1.5 × ULN	> 1.5 to 2.5 × ULN	> 2.5 to 5.0 × ULN	> 5.0 × ULN

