AST (SGOT)	1.25 to 2.50 × ULN	> 2.50 to 5.00 × ULN	> 5.00 to 10.00 × ULN	> 10.00 × ULN
ALT (SGPT)	1.25 to 2.50 × ULN	> 2.50 to 5.00 × ULN	> 5.00 to 10.00 × ULN	> 10.00 × ULN
GGT	1.25 to 2.50 × ULN	> 2.50 to 5.00 × ULN	> 5.00 to 10.00 × ULN	> 10.00 × ULN
Alkaline Phosphatase	1.25 to 2.50 × ULN	> 2.50 to 5.00 × ULN	> 5.00 to 10.00 × ULN	> 10.00 × ULN
Total Amylase	> 1.0 to 1.5 × ULN	> 1.5 to 2.0 × ULN	> 2.0 to 5.0 × ULN	> 5.0 × ULN
Pancreatic Amylase	> 1.0 to 1.5 × ULN	> 1.5 to 2.0 × ULN	> 2.0 to 5.0 × ULN	> 5.0 × ULN
Lipase	> 1.0 to 1.5 × ULN	> 1.5 to 3.0 × ULN	> 3.0 to 5.0 × ULN	> 5.0 × ULN
Albumin	-	2.0 to < LLN g/dL 20 to < LLN g/L	< 2.0 g/dL < 20 g/L	NA
Pediatrics <16 years				
≥ 16 years	3.0 g/dL to < LLN 30 g/L to < LLN	2.0 to < 3.0 g/dL 20 to < 30 g/L	< 2.0 g/dL < 20 g/L	NA

URINALYSIS				
	Grade 1	Grade 2	Grade 3	Grade 4
Hematuria (Dipstick)	1+	2+	3-4+	NA
Hematuria (Quantitative) See Note below				
Females	>ULN - 10 RBC/HPF	> 10-75 RBC/HPF	> 75 RBC/HPF	NA
Males	6-10 RBC/HPF	> 10-75 RBC/HPF	> 75 RBC/HPF	NA
Proteinuria (Dipstick)	1+	2-3+	4+	NA
Proteinuria, 24 Hour Collection				
Adult and Pediatric ≥ 10 Years	200 to 999 mg/24 h	>999 to 1999 mg/24 h	>1999 to 3500 mg/24 h	> 3500 mg/24 h
Pediatric > 3 Mo to < 10 Years	201 to 499 mg/m ² /24 h	>499 to 799 mg/m ² /24 h	>799 to 1000 mg/m ² /24 h	> 1000 mg/ m ² /24 h
Glycosuria (Dipstick)	1+	2-3+	4+	NA

Notes:

- Toxicity grades for Quantitative and Dipstick Hematuria will be assigned by Covance Laboratory, however for other laboratories, toxicity grades will only be assigned to Dipstick Hematuria.
- With the exception of lipid tests, any graded laboratory test with a result that is between the LLN and ULN should be assigned Grade 0.
- If the severity of a clinical AE could fall under either one of two grades (e.g., the severity of an AE could be either Grade 2 or Grade 3), select the higher of the two grades for the AE.

CARDIOVASCULAR				
	Grade 1	Grade 2	Grade 3	Grade 4
Cardiac Arrhythmia (general) (By ECG or physical exam)	Asymptomatic AND No intervention indicated	Asymptomatic AND Non-urgent medical intervention indicated	Symptomatic, non-life-threatening AND Non-urgent medical intervention indicated	Life-threatening arrhythmia OR Urgent intervention indicated
Cardiac-ischemia/Infarction	NA	NA	Symptomatic ischemia (stable angina) OR Testing consistent with ischemia	Unstable angina OR Acute myocardial infarction

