7.2.2. Graded Laboratory Values

The criteria specified in the protocol will be used to grade laboratory results as Grade 0, Grade 1 (mild), Grade 2 (moderate), Grade 3 (severe), or Grade 4 (life-threatening). Grade 0 includes all values that do not meet criteria for an abnormality of at least Grade 1. Some laboratory tests have criteria for both increased and decreased levels; analysis for each direction (ie, increased, decreased) will be presented separately.

If any laboratory toxicity grading scale overlaps with normal reference ranges (eg, Grade 1 scale overlaps with normal reference ranges), laboratory values within normal range will not be graded except for lipid tests.

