7.2.2.1. Treatment-Emergent Laboratory Abnormalities

Treatment-emergent laboratory abnormalities occurring in the double-blind phase are defined as values that increase by at least 1 toxicity grade from baseline at any postbaseline visit up to and including the minimum of the blinded study drug stop date + 3 days and the first dose date of open-label study drug, if applicable, for those who discontinued blinded study drug permanently, or values that increase by at least 1 toxicity grade from baseline at any post-baseline visit for those who are still on blinded study drug. If the relevant baseline laboratory value is missing, any laboratory abnormality of at least Grade 1 observed within the double-blind time frame specified above will be considered treatment emergent.

Treatment-emergent laboratory abnormalities occurring in the open-label phase are defined as values that increase by at least 1 toxicity grade from open-label baseline at any open-label postbaseline visit up to and including the last dose date of the open-label study drug + 3 days for those who discontinued open-label study drug permanently, or values that increase by at least 1 toxicity grade from open-label baseline at any open-label post-baseline visit for those who are still on open-label study drug. For the analyses of abnormalities occurring during open-label treatment, open-label baseline will be considered to be the last available record on or prior to Open-Label Study Drug 1.

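### Does counting confirmed low phosphorus only below 2.0 mg/dL leave paediatric Grade 2 and Grade 3 hypophosphataemia out of the safety report?

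*SAP*

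**What the plan says.** SAP 7.4.2 (Confirmed Renal Abnormalities) lists five laboratory criteria to be summarised for the double-blind phase: two for a confirmed rise in serum creatinine (at least 0.3 and at least 0.5 mg/dL above baseline), two for creatinine clearance (below 50 and below 70 mL/min), and one for phosphorus: "Confirmed (defined as 2 consecutive visits) occurrence of serum phosphorus below 2.0 mg/dL".

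The hypophosphataemia entry in Protocol Appendix 4 depends on age. For 1 to 14 years, Grade 1 is "3.0 to < LLN mg/dL 0.96 to < LLN mmol/L", Grade 2 is "2.5 to < 3.0 mg/dL 0.80 to < 0.96 mmol/L", Grade 3 is "1.5 to < 2.5 mg/dL 0.47 to < 0.80 mmol/L", and Grade 4 is anything below 1.5 mg/dL. For adults and children over 14, Grade 2 is "1.5 to < 2.0 mg/dL 0.47 to < 0.63 mmol/L".

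SAP 7.2.2 grades laboratory results by the protocol's criteria. SAP 7.2.2.1 defines a treatment-emergent abnormality in the double-blind phase by "values that increase by at least 1 toxicity grade from baseline at any postbaseline visit", within a stated time limit. SAP 7.2.2.3 tabulates these by treatment group and most severe grade, adds a Grade 3 and 4 table and a table of marked abnormalities, and lists the Grade 3 and 4 results.

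**The concern.** The cut-off of 2.0 mg/dL coincides with the upper limit of Grade 2 in the adult row and with no limit in the paediatric row. Two consecutive values of 2.4 mg/dL in a six-year-old are Grade 3 on the protocol's own scale, yet they do not enter the only phosphorus row that requires confirmation. That row could read zero in both arms while children had repeated Grade 2 or upper Grade 3 values.

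The analyte matters. Protocol 1.2.3.1.9 reports that 3 of the 4 renal discontinuations in the sponsor's paediatric HIV study were for hypophosphataemia. If the row were the plan's only account of low phosphorus, a tubular signal could be understated in the population where it is of most interest.

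**Working it through.** **1. Which age row applies.** Enrolment is below 12 years (Protocol 4.2). Baseline falls within 45 days of screening (Protocol 6.1.2), and some subjects were 12 by baseline (SAP 6.4). Some took blinded drug to Week 72 (SAP 4.3.2), and the Week 72 window closes on day 531 (SAP Table 3-2).

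- Oldest possible age at a double-blind sample: 12 + (45 + 531)/365.25 = 13.58 years.
- If the confirming sample falls at the end of the Week 80 window, day 587: 12 + (45 + 587)/365.25 = 13.73 years.

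Both are below 14, so the 1 to 14 years row applies throughout.

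**2. What the 7.4.2 row captures.**

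| Phosphorus, mg/dL | Grade, 1–14 years | Grade, over 14 and adult | In the 7.4.2 row if confirmed |
|---|---|---|---|
| below 1.0 | 4 | 4 | yes |
| 1.0 to <1.5 | 4 | 3 | yes |
| 1.5 to <2.0 | 3 | 2 | yes |
| 2.0 to <2.5 | 3 | 1 | no |
| 2.5 to <3.0 | 2 | 1 | no |

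The row takes none of paediatric Grade 2 and (2.0 − 1.5)/(2.5 − 1.5) = 0.5 of the width of Grade 3, pooled with Grade 4. The factual premise is correct.

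**3. Whether the band from 2.0 to 3.0 mg/dL goes unreported.** It does not.

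- *Graded tables (SAP 7.2.2.1 to 7.2.2.3).* One post-baseline value that is a grade worse than baseline is enough. Two consecutive such values contain one such value, so every confirmed worsening is already counted by arm, under that grade or a worse one. Paediatric Grade 3, including 2.0 to <2.5 mg/dL, also appears in the Grade 3 and 4 table and in the listing.
- *Normal-range rule.* Protocol Appendix 4 says "any graded laboratory test with a result that is between the LLN and ULN should be assigned Grade 0", and SAP 7.2.2 agrees: "laboratory values within normal range will not be graded except for lipid tests". The paediatric Grade 1 band runs from 3.0 up to the lower limit of normal, so it presupposes a limit above 3.0. The rule should seldom remove a value below 3.0. The documents do not state the limit.
- *Continuous data.* SAP 7.2.1 gives phosphorus by visit and arm, with change from baseline. SAP 7.3.2 compares fasting serum phosphate and the renal phosphate threshold between arms by Wilcoxon test up to Week 48.
- *Adverse events.* Protocol 7.5 requires a laboratory abnormality that is independent of the underlying condition and leads to interruption or discontinuation of drug to be recorded as an adverse event. SAP 7.1.6 tabulates both kinds by arm. Discontinuations for hypophosphataemia, the events cited from the HIV study, belong in that table and do not depend on the 7.4.2 row.

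**4. Whether a confirmed count by grade was promised.** Protocol 8.9.3 asks for treatment-emergent graded abnormalities by treatment group, and SAP 7.2.2 supplies them. Neither document promises confirmed counts by grade for any analyte. None of the other four criteria in SAP 7.4.2 is an Appendix 4 grade limit: Appendix 4 grades creatinine on absolute values starting above 1.50 mg/dL and has no creatinine-clearance entry. A fixed 2.0 mg/dL row also has a precedent, since Protocol 1.2.3.1.1 reports confirmed phosphorus below 2 mg/dL in the adult hepatitis B trials.

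**The case for a change.** The strongest reply is that an unconfirmed count cannot stand in for a confirmed one. Assume, since the documents give no rates, a 1% to 5% chance at each visit of a value below 3.0 mg/dL.

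- **Independent visits, 7 visits to Week 48, 1%:** at least one low value 1 − 0.99^7 = 6.79%; two in a row 0.059%. Ratio 0.059/6.79, about 1%.
- **A low value has a 50% chance of being low again, 10 visits to Week 72, 5%:** at least one 25.27%; two in a row 12.17%. Ratio 48%.
- **The same persistent case under the SAP 7.4.2 confirmation rules:** if the next visit after the blinded phase may confirm, 13.3/25.3 = 53%. If a low last value with no later assessment counts, 14.4/25.3 = 57%; with 7 visits, 11.0/19.0 = 58%.

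The confirmed count could thus be anywhere from about 1% to 58% of the graded count, and a reader could not deduce one from the other. That stands, as does the point that a listing is not a count by arm. The subset argument also has an exception: a child already at the same grade at baseline is not treatment-emergent, so persistent low phosphorus in that child shows only in the visit summaries and listings.

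None of this makes the plan wrong. The range comes from assumed inputs and shows only that two definitions give different numbers. The graded table is the more inclusive of the two for worsening from baseline, so it cannot hide a signal that the confirmed count would reveal. A zero row in 7.4.2 misleads only a reader who passes over the graded table in the same report.

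**Conclusion.** The concern does not hold. The 2.0 mg/dL row does not match the paediatric grades, but it does not claim to, and the plan does not rely on it to report paediatric hypophosphataemia. Paediatric-graded counts by arm, a Grade 3 and 4 table and listing, between-arm comparisons of fasting phosphate and renal phosphate threshold, and adverse-event tables all cover the ground. Confirmed counts at the paediatric limits would be a presentational extra in a descriptive table.

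What the plan does not give is a confirmed count by arm between 2.0 and 3.0 mg/dL. The number of children affected cannot be derived from the documents. No efficacy result, hypothesis test or safety conclusion turns on it. The conclusion assumes that the graded tables use the 1 to 14 years row, as Appendix 4 requires at these ages, and that the laboratory's lower limit of normal lies above 3.0 mg/dL, as the Grade 1 band implies.

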6.2.2. Week 48 Assessments – End of Blinded Randomized Treatment

Study Visit for Week 48 should be completed ± 4 days of the protocol-specified visit date, based on the Baseline Visit. The following assessments and procedures will be performed and recorded on CRFs:

- Complete physical examination including Tanner Staging and vital signs
- Body weight and height
- Blood samples for:
 - Hematology (CBC with differential and platelet count)
 - Serum chemistry and liver function tests, including albumin, alkaline phosphatase, AST, ALT, total bilirubin (reflex to direct [conjugated] bilirubin if total bilirubin $> 1.5 \times$ ULN), bicarbonate, BUN, calcium, chloride, CPK, creatinine (and calculated creatinine clearance), glucose, LDH, magnesium, phosphorus, potassium, sodium, uric acid, and amylase (reflex lipase testing if total amylase is $\geq 1.5 \times$ ULN)
 - Serum bone biochemical markers, including serum c-telopeptides, osteocalcin, bone-specific alkaline phosphatase, PTH, vitamin D levels (25-hydroxy), 1,25 (dihydroxyvitamin) D levels, and fasting creatinine and fasting phosphate
 - Hepatitis B serology (HBeAg and HBsAg; reflex HBeAb and HBsAb if Ag negative)
 - Plasma HBV DNA (PCR method)
 - Serum β -HCG pregnancy test (females of childbearing potential only)
 - Serum for resistance surveillance
 - Plasma for determination of tenofovir concentration
 - Serum and plasma for storage (for potential pharmacokinetic and/or virologic assays, including resistance surveillance, HBsAg and HBeAg quantification and compliance assessment)

- Urine samples for:
 - Urinalysis (protein, glucose, blood)
 - Urine bone biochemical markers, including urine bicarbonate, urine n-telopeptide, and spot urine creatinine and phosphate
- DEXA scan of spine and whole body (DEXA scans may be performed \pm 10 days from the Week 48 visit).
- Review of AEs and concomitant medications
- Retrieval of study medication and assessment of medication adherence
- Study drug dispensing (including multivitamin) and instructions on appropriate dosing and administration

After 48 weeks of blinded randomized treatment, each subject will switch to open-label tenofovir DF treatment for an additional 144 weeks. Subjects under Protocol Amendment 3 who are beyond Week 48 of blinded randomized treatment will switch to open-label tenofovir DF at the Week 72 visit and will continue on open-label treatment until Week 192.

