Subjects who discontinue the study prior to the Week 48 Visit will complete an Early Study Drug Discontinuation Visit as detailed in Section 6.3. Subsequent off-study therapy, if any, is at the discretion of the subject/physician and will not be provided by Gilead Sciences. Subjects who have received at least one dose of study drug and permanently discontinue study drug will be followed for 24 weeks off treatment or up to initiation of active treatment, whichever occurs first.

6.2.3. Assessments for Weeks 56, 64, 72, 80, 88, 96, 108, 120, 132, 144, 156, 168, 180, and Extension Phase

After Week 48 through the end of the study treatment (Week 192), subjects will return for visits at Weeks 56, 64, 72, 80, 88, 96, 108, 120, 132, 144, 156, 168, and 180. Each study visit will occur \pm 6 days from the protocol-specified visit date, based on the Baseline Visit.

Subjects in this study who complete all study visits and are on tenofovir DF at the Week 192 visit will be eligible to continue in the Extension Phase of the study, where they will receive open-label tenofovir DF (dose adjusted for weight) until Viread is commercially available in that country for treatment of Chronic HBV in patients of their age and weight. During the Extension Phase, subjects will return for visits every 12 weeks to assess efficacy and safety, to conduct study drug accountability, and dispense study drug. Study Visits for the Extension Phase should be completed within \pm 14 days of the protocol-specified visit date, based on the Baseline Visit. When commercial Viread becomes available, subjects will complete the End of Treatment Visit assessments at the next scheduled visit (see Section 6.2.4), and the subject's participation in the study will end.

The following assessments and procedures will be performed during these visits and recorded on CRFs:

- Symptom-directed physical examination, including vital signs (complete physical examination including Tanner Staging at Weeks 72, 96, 120, 144, 168, and every 48 weeks during Extension Phase)
- Body weight and height
- Blood samples for:
 - Hematology (CBC with differential and platelet count)

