At screening, pediatric subjects (2 to < 12 years of age) with chronic HBeAg-positive or HBeAg-negative HBV infection (hepatitis B surface antigen [HBsAg]-positive for at least 6 months; with HBV DNA $\geq 10^5$ copies/mL, ALT $\geq 1.5 \times$ ULN and creatinine clearance ≥ 80 mL/min/1.73 m² at screening by the Schwartz formula) will be eligible for the study. Subjects must be naive to TDF, but could have received interferon-alfa and/or other oral anti-HBV nucleoside/nucleotide therapies. Subjects experienced on oral anti-HBV nucleoside/nucleotide therapy must have discontinued therapy ≥ 16 weeks prior to screening (in order to avoid on-treatment ALT flare if randomized to receive placebo treatment). Subjects must have discontinued interferon-alfa ≥ 6 months prior to screening. Subjects must be without evidence of co-infection with human immunodeficiency virus (HIV), hepatitis C virus (HCV), hepatitis D virus (HDV) or acute hepatitis A virus (HAV). Subjects with a history of significant renal disease, bone disease, decompensated liver disease, evidence of hepatocellular carcinoma (ie, α fetoprotein > 50 ng/mL), or any chronic liver disease not related to HBV infection will not be eligible for the study.

Study Periods/Phases

The duration of randomized, double-blind treatment is 48 weeks.

As per Protocol Amendment 4, after 48 weeks of blinded randomized treatment, each subject will switch to open-label TDF treatment for an additional 144 weeks (ie through Week 192). Subjects under Protocol Amendment 3, wherein the primary analysis was planned for Week 72, who were treated beyond Week 48 of blinded randomized treatment, were to switch to open-label TDF at the Week 72 visit and then continue on open-label treatment until Week 192. Total study drug treatment period is 192 weeks for all enrolled subjects.

After the completion of the Week 192 visit, all subjects who have completed the study will be offered open-label TDF under the Extension Phase of the protocol. Subjects who permanently discontinue study drug or complete the study at Week 192 and do not enter the Extension Phase will be followed for 24 weeks off treatment or up to initiation of active treatment, whichever occurs first. Subjects who enter the Extension Phase after completion of the study at Week 192 will be offered open label TDF and followed every 12 weeks until TDF is commercially available in that country for treatment of chronic HBV in subjects of their age and weight.

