7.2.3. ALT Flare and Exacerbation of Hepatitis

Summaries of the incidence of ALT flare and exacerbation of hepatitis will be provided by treatment group using the subjects in the Safety Analysis Set for on-treatment occurrences during the double-blind phase and off-treatment occurrences. On-treatment occurrences in the double-blind phase will be defined as occurrences in the period between the first dose of blinded study drug to the minimum of the last dose date of blinded study drug + 3 days and first dose date of open-label study drug, if applicable, for those who discontinued blinded study drug permanently. Off-treatment occurrences will be defined as occurrences after the last dose of study drug + 3 days. A supportive listing will also be generated.

Incidence of ALT flare and exacerbation of hepatitis is defined as:

- Serum ALT $> 2 \times$ study baseline and $> 10 \times$ ULN, with or without associated symptoms

OR

- Confirmed ALT elevation (defined as 1 grade shift [ie, increase] or $2 \times$ previous value) with confirmed changes outside of the normal range in other laboratory parameters suggestive of worsening hepatic function (abnormal prothrombin time ≥ 2 seconds over study baseline or international normalized ratio [INR] ≥ 0.5 over study baseline, and abnormal serum albumin ≥ 1 g/dL below study baseline or elevated serum lactate levels [if available], defined as $2 \times$ ULN).

If the first of two consecutive results is in the double-blind phase and the second is out of the double-blind phase (ie, in the open-label or TFFU phase), then the result will be considered to be confirmed in the double-blind phase (assuming both values meet the criterion). And if the criterion is met by the last value in the double-blind phase, and no assessments are available after due to the subject exiting the study or data not yet available (eg, due to the data-cut), then the result will also be considered to be confirmed.

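### Renal abnormalities (and one limb of ALT flare) first met at the last blinded result can be confirmed or refuted after the switch to open-label TDF, a treatment change for placebo children only; these cases should be shown separately (minor)

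*SAP*

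**What the plan says.** SAP 7.4.2 lists five renal rows for the double-blind phase. Three need confirmation: creatinine up by at least 0.3 mg/dL, creatinine up by at least 0.5 mg/dL, and phosphorus below 2.0 mg/dL. The first reads "Confirmed (defined as 2 consecutive visits) increase in serum creatinine of ≥ 0.3 mg/dL above baseline". The two Schwartz clearance rows (below 50 and below 70 mL/min) carry no such condition.

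The section then deals with the end of blinding: "If the first of two consecutive results is in the double-blind phase and the second is out of the double-blind phase", which it explains as the open-label or treatment-free follow-up (TFFU) phase, "then the result will be considered to be confirmed in the double-blind phase (assuming both values meet the criterion"). If the last double-blind value qualifies and no later value exists, because the child left or the data cut came first, the event also counts as confirmed.

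SAP 7.2.3 repeats both rules for ALT flare. Its first criterion (ALT above 2 × baseline and above 10 × ULN) stands on one value. Its second needs a confirmed ALT elevation together with confirmed changes in other hepatic tests.

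On treatment, Protocol 6.2.2 says: "After 48 weeks of blinded randomized treatment, each subject will switch to open-label tenofovir DF treatment for an additional 144 weeks". Children treated blind beyond Week 48 "were to switch to open-label TDF at the Week 72 visit and then continue on open-label treatment until Week 192" (SAP 1.2). On visits after Week 48, Protocol 6.2.3 says "subjects will return for visits at Weeks 56, 64, 72, 80, 88, 96", then every 12 weeks.

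**The concern.** A confirmation rule is meant to separate a persistent abnormality from a chance one while treatment stays the same. Here the wording is the same for both arms but the test is not. A placebo child's last-visit value is checked on the drug under study, and a TDF child's on unchanged drug.

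The rule also departs from the SAP's own boundary. Sections 3.8.2, 7.2.2.1 and 7.2.2.2 close the double-blind laboratory period no later than the first open-label dose. Section 7.11 explains the three-day extension after stopping drug, but not the use of post-switch samples. No summary or sensitivity analysis separates these cases.

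What is at stake is the between-arm reading of the blinded renal table and, marginally, the flare table. Protocol 1.3 names renal safety as one reason for having a placebo arm.

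**Working it through.** The plan gives no figure on this point to reproduce. The check traces the rule against the switch and visit schedules.

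**1. Criteria that depend on a second sample.** Renal: 3 of 5. ALT flare: 1 of 2.

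**2. When the second sample is drawn.** Week 48 samples go to a central laboratory (Protocol 6), and drug for the next period is dispensed at that visit (Protocol 6.2.2). The next scheduled chemistry is at Week 56: (56 − 48) × 7 = 56 days. After a Week 72 switch it is at Week 80: (80 − 72) × 7 = 56 days. Earlier repeats are timed as follows:
- within 3 calendar days of receiving the result, for clinically significant Grade 3–4 values (Protocol 7.6);
- within the same time, for clearance below 70 with creatinine up by at least 0.5 mg/dL (Protocol 7.6.4);
- ideally within a week of the initial sample, for a suspected ALT flare (Protocol 7.6.6.1).

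These come after days rather than weeks of open-label drug, but normally still after the switch.

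**3. Treatment at the first and second sample.**

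| After the last blinded result | TDF arm | Placebo arm |
|---|---|---|
| Enters open-label | TDF, then TDF | placebo, then TDF |
| Stops, enters TFFU | TDF, then none | placebo, then none |
| No later value | counted on one value | counted on one value |

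Treatment changes for placebo in the first row and for TDF in the second. The third row means that, at the Week 48 data cut, a recently enrolled child with no Week 56 result is counted automatically. An earlier child with the same Week 48 value must be confirmed on TDF.

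**4. Share of visits affected.** For a Week 48 switch there are 7 scheduled post-baseline blinded chemistries (Weeks 4, 8, 16, 24, 32, 40, 48), and the last is the boundary one: 1/7 = 14.3%. For a Week 72 switch, Weeks 56, 64 and 72 are added: 1/10 = 10%. Reading these as shares of confirmation opportunities assumes equal risk at each visit.

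**5. Weight of one event.** SAP 1.3 gives 90 randomized and 89 treated. If 2:1 held, placebo is about 90/3 = 30, so one child is 1/30 = 3.3 percentage points.

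**6. Illustration, with inputs that are assumptions.** Let p be the proportion of placebo children first meeting a criterion at the last blinded visit (1% to 5%), and d the change in the chance of confirmation caused by the switch (25 to 50 points, either sign). The change in the expected placebo count is 30 × p × d:
- smallest: 30 × 0.01 × 0.25 = 0.075 children;
- largest: 30 × 0.05 × 0.50 = 0.75 children.

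**The case against.** **The hepatic part is nearly empty.** The large-flare criterion needs no second sample. As SAP 7.2.3 words it, the confirmed limb also needs a PT or INR change and an albumin or lactate change. PT/INR is scheduled only at Screening and Baseline and is a reflex test thereafter (Protocol Appendix 2, note j); lactate is not a scheduled test. This stands: the count of seven visits does not describe that limb.

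**Repeats often come within days.** Phosphorus below 2.0 mg/dL is at least Grade 3 at ages 1 to 14 (Protocol Appendix 4), so a clinically significant value is repeated promptly, as is a large creatinine rise with clearance below 70. This largely stands, and the eight-week wait mainly concerns the creatinine +0.3 row. One gap remains: the rows define confirmation by consecutive visits and the boundary rule by consecutive results, so it is not spelled out whether an unscheduled repeat qualifies.

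**Other analyses do not need confirmation.** Treatment-emergent laboratory grades stop at the first open-label dose, eGFR change is compared directly, and listings include open-label data. This also stands, although it helps the creatinine rows less: Appendix 4 grades creatinine only above 1.50 mg/dL, so a 0.5 rise from a baseline of 1.0 or less (1.0 + 0.5 = 1.50) goes ungraded.

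**Stronger readings are not supported.** A reader might infer that the rule hides TDF renal toxicity by charging it to placebo, or hides placebo flares. The documents do not fix a direction. For Study GS-US-104-0352, Protocol 1.2.3.1.9 reports no clinically relevant renal difference in the randomized period, but also four later renal discontinuations. A reader might also assume that TDF doubles the chance of renal confirmation and conclude that a quarter of placebo events are spurious: 2/(6 + 2) = 25%. That is the boundary pair's share, not the bias. The total would rise by (6 + 2)/7 − 1 = 14%, and the doubling itself has no source in the documents.

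**Conclusion.** The point holds as a minor interpretive weakness. For three renal rows, and to a much lesser extent one ALT-flare limb, an abnormality first met at the last blinded result may be confirmed or refuted under a treatment that has changed in one arm only. That is the placebo arm for children who roll over and the TDF arm for those who enter TFFU. The two clearance rows and the large-flare criterion are unaffected, as is any abnormality that already has a second double-blind result. The primary efficacy analysis is not touched.

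The expected effect is below one placebo child under the assumed ranges, in either direction, and SAP 7.4.2 and 7.2.3 specify only incidence summaries. It still merits a line in the SAP because a single placebo event moves its row by about 3.3 points, taking the 2:1 ratio to have held.

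**What to change.** Keep the existing rule. In SAP 7.2.3 and 7.4.2, add a summary by arm of abnormalities first met at the last blinded result with no second double-blind result, split into:

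- (a) confirmed only by a sample after the first open-label dose or in TFFU;
- (b) not confirmed by such a sample;
- (c) counted as confirmed because no later value exists.

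Show the confirmed-event counts with and without these cases. Leaving out (a) and (c) gives a count resting on double-blind pairs alone. Adding (b) to the existing count shows the result had every such abnormality been counted. Neither depends on a sample taken after treatment changed, so the two bracket the rule's result.

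Specify this before unblinding; with so few events, a later choice would look data-driven. The cost is one or two extra rows in descriptive tables. Replacing the rule so that every last-visit value counts as confirmed is not needed. It would discard a real second result, including in TDF children whose treatment did not change, and would put single-value events into a table labelled confirmed.
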